3) Inclusion and Exclusion Criteria***A. Inclusion Criteria**

To be eligible participants should:

- Diagnosed with HIV (based on self-report).
- Be 18 years and older
- Have smoked ≥ 5 cigarettes/day in the past year

- Be interested in making a quit attempt in the next 30 days
- Own a smartphone (apple/android), and plan to keep it active for the next 6 months
- Able to consent
- Have no plans to move in the next 6 months
- Are not pregnant or planning to be pregnant in the following 6 months
- Have any condition that, in the opinion of the investigator, would compromise the well-being of the patient or the study or prevent the patient from meeting or performing study requirements

B. Exclusion Criteria

Participants would be excluded if they:

- Have contraindication to NRT (past month myocardial infarction, history of serious arrhythmias/or unstable angina pectoris, dermatological disorder)
- Are currently being treated for a psychiatric condition.
- Are currently being treated for smoking cessation, alcoholism, or illicit drug use
- Are adults unable to consent
- Are individuals who are not yet adults
- Are pregnant women
- Are prisoners

4) Study Design

- a. Study Type – Interventional
- b. Primary Purpose – Other
- c. Interventional Study Model – Sequential
- d. Number of Arms – 2
- e. Randomized or not – Randomized
- f. Open label or if blinded – Not blinded
- g. Number of participants – 100

5) Procedures Involved*

We will recruit participants via community and clinic flyers and among participants of another on-going survey who smoke (IRB#20180269). In Stage 1, participants will be randomized into one of two groups: 1) a group mindfulness training (MT) for smoking cessation, or 2) contingency management (CM) for smoking cessation. In Stage 2 non-

responders (those who have not quit at 1 month evaluation) will be randomized to: 1) *Switch* to sequentially receive the other intervention (i.e., CM or MI) and complete the 3-month assessment; or 2) *Continue* without further intervention and complete the 3-month assessment only.

In stage 1, both groups will do the following:

- Complete a baseline survey.
- Receive 6 weeks of Nicotine Replacement Treatment (NRT) via mail
- Receive reminder/encouragement calls or texts the day before their quit date and 2 weeks after their quit date.

Arm 1: The MT smoking cessation intervention:

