- *Demographics and HIV history:* Age, race/ethnicity, birth origin, years in USA, relationship status, education, employment, income, acculturation, discrimination, self-identity, time since HIV diagnosis, HIV treatment.

Smoking status will be verified using breath carbon monoxide (CO [< 8 parts per million (ppm)], which can be determined quickly through a small, hand-held monitor and/or using a saliva screening test (cutoff concentration of ≤ 30 ng/mL), which can be determined quickly through a NicoTests saliva sample.

- *Smoking:* Smoking history, past quit attempt, motivation to quit, confidence in quitting, Fagerström test for nicotine dependence,^[15] 12-item smoking self-efficacy to resist urge to smoke,^[16] and 15-item Minnesota nicotine withdrawal scale (i.e., craving, irritability, anxiety, depression).^[17]

- *Mindfulness skills:* The 15-item short form five facets of mindfulness questionnaire that measures MT skills related to observing, describing, acting with awareness, non-judging of inner experience, and non-reactivity to inner experience.^[18]

- *Others:* The 20-item Centers for the Epidemiologic Study of Depression (CES-D) scale,^[19] social support,^[20] quality of life,^[21] and alcohol and substance use (ASSIST).^[22]

2. End-of treatment assessment (one month after quit date):

- The follow up assessment will occur at 1 months after quit date. The visit will last approximately 45 minutes.

- Information on number of sessions that was attended.

- *Acceptability:* The acceptability will be assessed by 3 items “How satisfied were you with the intervention?”, “How likely are you to recommend this intervention to a friend?” and “How useful was the intervention?”

Smoking Cessation: Main smoking cessation outcome is 7-day point-prevalence abstinence (defined as self-report of not smoking in the past 7-days; not even a puff) and confirmed smoking cessation by expired carbon monoxide (CO) level cutoff of < 8 ppm using a coVita iCO™ Smokerlyzer® and/or NicoTests saliva sample of ≤ 30 ng/mL at the 1-month follow up. Secondary outcomes include the reduction in number of cigarettes smoked per day.^[23,24] Relapse is defined as smoking at least once/week on two consecutive weeks.^[25] These are described in more detail below.

3. Three-month Follow-up Assessment (3-month after quit date):

- The follow up assessment will occur at 3 months (+30 days) after quit date. The visit will last approximately 45 minutes.

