- All baseline assessment will be re-administered except demographics.

- Information on number of sessions that was attended.
- *Acceptability:* The acceptability will be assessed by 3 items “How satisfied were you with the intervention?”, “How likely are you to recommend this intervention to a friend?” and “How useful was the intervention?”
- *Smoking Cessation:* Main smoking cessation outcome is 7-day point-prevalence abstinence (defined as self-report of not smoking in the past 7-days; not even a puff) and confirmed smoking cessation by expired carbon monoxide (CO) level cutoff of < 8 ppm using a coVita iCO™ Smokerlyzer® and/or NicoTests saliva sample of ≤ 30 ng/mL at the 3-month follow up. Secondary outcomes include the reduction in number of cigarettes smoked per day.[23,24] Relapse is defined as smoking at least once/week on two consecutive weeks.[25] These are described in more detail below.
- *Process evaluation:* Semi-structured post-intervention evaluation interviews will be conducted with randomly selected participants to further inform our assessment of acceptability and perceived helpfulness of interventions, and identifying key areas for refining the intervention protocols (e.g., improving access, content, usability). These will be conducted in-person or via Zoom and participants will receive \$25 for completing the interview.

Primary Outcome Measure Title: Smoking cessation - 7-day point-prevalence abstinence.

Outcome Measure Description:

Defined as self-report of not smoking in the past 7-days, not even a puff and confirmed by expired carbon monoxide (CO) level cutoff of < 8 ppm using a coVita iCO™ Smokerlyzer® and/or NicoTests saliva sample of ≤ 30 ng/mL.

Outcome Measure Timeframe:

4 weeks (end of treatment), and 3 months

Secondary Outcomes

1. Treatment-specific retention rates for study measures.
 - Defined as: Percentage of participants completing all study procedures divided by total enrolled. Coded reasons for dropouts.
 - Timeframe: 3 months
2. Treatment-specific adherence rates to study protocol
 - Defined as number of phone-call check-ins attended by each participant (4 for mindfulness training, 12 for contingency management).
 - Timeframe: 3 months

6) Data and Specimen Banking*

There will be no data or specimen banking.

7) Data Management*

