The analysis of the feasibility and acceptability outcomes will be mainly descriptive. We will calculate differences in pre and post intervention measures of baseline characteristics, indices of treatment implementation, adherence, retention, and treatment perceptions and compare the differences between arms 1 and 2. Attrition analyses will compare respondents who complete all measurements to those who do not based on baseline characteristics. Direct maximum likelihood estimation and multiple imputation will be used to address incomplete data. Univariate and multivariable logistic regression models will be used to explore baseline predictors of 3-month smoking cessation and the acceptability and feasibility of the intervention. Cross-tabulations for ordinal variables and mean and corresponding 95% confidence intervals for continuous variables will be used to explore secondary outcomes including improvement in depression, smoking self-efficacy, craving, quality of life, and mindfulness skills. Although we are unpowered to detect differences by gender, we will consider exploring the gender effect on our main outcomes in our analysis. Data management for preparing data for statistical analysis and statistical analysis will be performed with SAS or R statistical software.

Qualitative analyses of semi-structured post-intervention evaluation interviews will identify emergent themes related to acceptability and specific targets for refinement of content and delivery. Interviews will be audio-recorded, transcribed verbatim, and analyzed using Nvivo. This program is designed for the storage, coding, retrieval, and analysis of qualitative data. Two complementary coding schemes will be used: 1) descriptive, which uses words or short phrases to summarize passages of data and 2) in Nvivo, in which actual language from participants is used to name concepts and themes. Extensive analytic memos will be written after each interview is conducted, coded, and throughout the analysis process to reflect on code choices, emergent themes and patterns, and conceptual models. Finally, the data will be themed, in which the final sets of codes and their meanings will be transformed into longer and more descriptive themes to organize recurrent meanings and patterns. Themes and definitions will be compared across interviews to ensure consistency and reliability.

Statistical analyses will be done using SPSS, V21, (<https://www.ibm.com/analytics/spss-statistics-software>).

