Our team of multi-disciplinary experts in smoking cessation, MT, and analysis is a pioneer in developing and testing novel smoking cessation interventions among high-risk populations. Drs. [name] and [name] have long-term collaboration on several epidemiological studies and community-based cessation trials.[26-28] [name] (PI) is a Research Assistant Professor in the Department of Public Health Sciences at the University of Miami (UM). She has more than 10 years of experience in tobacco research. She had led several clinical- and community-based smoking cessation trials.[29-32] [name] (Co-I) has been involved in tobacco research for over 20 years. Recently, he has been evaluating mindfulness-based interventions

targeting high-stress occupational groups, and he will assist [name] in the development and testing of the proposed intervention.

14) Prior Approvals

N/A

15) Recruitment Methods

Our target sample size is up to 100 HIV patients who smoke (50 in each arm). Flyers will also be distributed at UM/HIV clinics and various community-based clinics/organizations not directly affiliated with UM/HIV, such as Jackson Health System (JHS). We will also recruit via advertisements on social media platforms.

Those interested will contact our research team to first determine eligibility or they may scan the QR code included on the study flyer to complete the screening questions independently via REDCap. Those completing the screening questions independently via REDCap will be assigned a subject ID and will then be directed to a separate form asking for their name and contact information, in case needed to be reached. If eligible, the research staff will provide an overview of the research study, and if the participant wants to participate, we will send them a link to complete the electronic informed consent and baseline survey via REDCap.

We are requesting permission to collaborate with another study, Project CHARM (IRB#20160911), which serves as a consent to contact database, to contact eligible participants. They will provide us with contact information for participants in their study who might be eligible for our study and have consented to be contacted by other studies.

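### At 3 months, Switch participants rate an unnamed intervention after being assigned both, and section 7 does not say which visit the arm comparison of acceptability uses

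*Combined protocol and SAP*

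**What the plan says.** Section 5 (Procedures Involved, Study measures) schedules the same three acceptability items at two visits. They cover satisfaction, willingness to recommend, and usefulness. The first visit is the "End-of treatment assessment (one month after quit date"); the second is the three-month follow-up. At both, the wording refers to one intervention without naming it, for example "How satisfied were you with the intervention".

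Between these visits comes Stage 2. Section 5 says that non-"responders (those who have not quit at 1 month evaluation) will be randomized to" one of two options (a page break splits off the prefix). Under Switch they are "to sequentially receive the other intervention (i.e., CM or MI) and complete the 3-month assessment". I read MI there as MT, since section 5 describes no intervention called MI. Under Continue they go on "without further intervention and complete the 3-month assessment only".

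Section 7 (Data Management) states: "The analysis of the feasibility and acceptability outcomes will be mainly descriptive". Among the planned summaries it lists "treatment perceptions and compare the differences between arms 1 and 2". It names no visit for this comparison and gives no rule for participants who switched.

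**The concern.** A Switch participant reaches the 3-month visit having been assigned two interventions, the more recent being the one not first allocated. Asked about a single unnamed intervention, that person may rate the first, the second, or some blend. The answer does not show which.

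Two things are at stake. First, the 3-month items are the only scheduled item ratings of MT given after CM, or of CM given after MT. A pilot SMART whose objective is to find the best dynamic strategy has a use for that information, and section 2 (Background) names acceptability among the things to be tested. Second, an analyst following section 7 could compare 3-month ratings by Stage 1 arm. A switcher's view of CM could then be counted as acceptability of MT, and the reverse.

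**Working it through.** **Who is affected**

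| Group | Assigned by 1 month | Assigned by 3 months | 3-month rating attributable? |
|---|---|---|---|
| Responders | one intervention | one | yes |
| Non-responders, Continue | one | one | yes |
| Non-responders, Switch | one | both | no |

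Stage 2 allocation depends on the 1-month evaluation, so every 1-month rating refers to one intervention. Section 5 also places an end-of-treatment assessment two weeks after the intervention ends. I take this to be the same visit as the one-month assessment, because the Stage 2 text lists only the 3-month assessment for switchers.

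**Inputs**

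- From the documents (section 15, Recruitment Methods): "Our target sample size is up to 100 HIV patients who smoke (50 in each arm"). There is no planned figure for acceptability to reproduce.
- Not in the documents, so assumed: non-response q of 50%, 70% or 90%; 1:1 Stage 2 allocation; equal retention; the same mean rating of each intervention in switchers and non-switchers.

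**Effect on a 3-month comparison by original arm**

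Let a and b be the true mean ratings of MT and CM, and δ = a − b. Let s1 and s2 be the shares of arms 1 and 2 that switch (s = q/2). Let w be the weight a switcher gives to the second intervention: 1 for the latest only, 0.5 for an average, 0 for the first only.

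- Arm 1 mean = (1 − w·s1)a + w·s1·b
- Arm 2 mean = (1 − w·s2)b + w·s2·a
- Difference = (1 − w·s1 − w·s2)δ, which is (1 − 2ws)δ when s1 = s2 = s

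| q in both arms | s | Switchers per 50 | Latest: 1 − 2s | Average: 1 − s | First |
|---|---|---|---|---|---|
| 50% | 0.25 | 12.5 | 0.50 | 0.75 | 1.0 |
| 70% | 0.35 | 17.5 | 0.30 | 0.65 | 1.0 |
| 90% | 0.45 | 22.5 | 0.10 | 0.55 | 1.0 |

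**Is the pull always toward zero?**

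No. Suppose switchers' ratings shift by c1 in arm 1 and c2 in arm 2 because of order or contrast. This adds c1·s1 − c2·s2 to the difference. All values below are assumed, in SD units, with switchers rating the latest intervention.

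- Non-response 90% and 50% (s1 = 0.45, s2 = 0.25), both shifts +1: δ = 0 becomes 0.45 − 0.25 = 0.20, and δ = 0.2 becomes 0.30 × 0.2 + 0.20 = 0.26.
- s1 = s2 = 0.35, δ = 0.3, shifts +0.5 and −0.5: 0.30 × 0.3 + 0.35 × 1.0 = 0.44.
- The same with shifts −0.3 and +0.3: 0.09 − 0.35 × 0.6 = −0.12.

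The difference can therefore shrink, grow or change sign.

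**The case against.** The strongest reply is that the plan already collects what the arm comparison needs. The identical items at 1 month give attributable ratings of MT and CM in both arms before anyone switches. Section 7 does not say that the 3-month ratings are the ones compared, and it does not define treatment perceptions as these three items. This stands. A reader might infer that acceptability of MT and CM cannot be compared at all, or that the planned comparison is biased. The documents support neither; they support only that the visit is unspecified.

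A reader might also infer that all non-responders cross over. They do not, since those allocated to Continue receive nothing further.

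It can also be said that Stage 2 allocation is known, so 3-month ratings can be tabulated by sequence, and that interviews will explore acceptability. Tabulating by sequence isolates the switchers but does not show which intervention each one rated. The interviews cover a random subset of unstated size and are analyzed for themes, so they supplement labelled ratings without replacing them.

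Finally, materiality is limited. Acceptability is not among the listed primary or secondary outcomes in section 5, section 1 (Objectives) is about confirmed abstinence, and the acceptability analysis carries no test or threshold. This also stands and keeps the importance modest.

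**Conclusion.** The point holds for Switch participants at 3 months. Followed exactly, the plan yields second-stage ratings that cannot be assigned to MT or CM, and no later tabulation repairs the wording. Section 7 also leaves open a comparison that would mix treatments.

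The size is conditional. The retained fractions of 0.10 to 0.50 (latest), 0.55 to 0.75 (average) and 1.0 (first) rest on assumed non-response, a 1:1 Stage 2 split, equal switching and retention in both arms, and no order effects. A reader might infer that the arm difference must be pulled toward zero. That follows only under these assumptions and only if switchers give some weight to the second intervention; otherwise the direction is unknown. No conclusion about abstinence depends on this. It is an inexpensive improvement of modest importance.

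**What to change.** 1. In section 5, three-month follow-up: name the intervention in each acceptability item (for example *the mindfulness sessions*, or *the contingency management check-ins and rewards*) and ask the three items once for each intervention received.
2. In section 7: state that the arm 1 versus arm 2 comparison of acceptability uses the 1-month items, which precede any switch.
3. In section 7: state that the 3-month items are reported by intervention and by treatment sequence.

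The cost is three extra short items for Switch participants, branching in REDCap (already the data capture system), and a sentence or two in section 7. With labelled items, or with the 1-month items, the dilution calculated above does not arise, and no figure in the plan changes.

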Protocol Title

A Pilot SMART Testing an Integrative Smoking Cessation Intervention for HIV Patients

Protocol Number:

20201296

Protocol Version

12

Protocol Version Date

10/6/23

Principal Investigator

[name], MSPH, MD

NCT Number

NCT05030766

1) Objectives*

We will conduct a pilot Sequential, Multiple Assignment randomized clinical trial (SMART) incorporating nicotine replacement treatment (NRT), contingency management (CM), and mindfulness training (MT) to identify the optimal dynamic strategy to promote biomarker-confirmed smoking abstinence among people living with HIV (PLWH).

2) Background*

Mindfulness training (MT) is an approach that has become more widely used for the purposes of smoking cessation. MT can operationalized into two components: 1) maintaining attention on immediate experience, and 2) maintaining an attitude of acceptance toward that experience, which can improve individuals' ability to avoid absorption in maladaptive mental patterns, behaviors, and emotional reactions that lead to depression.[1,2] [ENREF 40](#) MT is effective in reducing both self-report and objective indices of negative affect and psychological stress.[3,4] MT also can help smokers control craving by being less emotionally reactive and less prone to relapse related to avoidance of distressing symptoms.[5] The use of MT for smoking cessation, however, has not been tested among Hispanics HIV patients who smoke. We, therefore, propose to test the feasibility, acceptability, and potential efficacy of a mindfulness smoking cessation intervention among Hispanics HIV patients that smoke. CM is an evidence-based behavioral intervention where individuals receive escalating tangible reinforcement for biologically confirmed substance abstinence.[6] CM has been successful in retaining patients in treatment and fostering stable periods of abstinence in substance use behavioral research, including tobacco.[7-9] In HIV patients, CM was feasible and effective in improving compliance to ART[10] and reducing HIV risk behaviors (e.g., unprotected sex, injection drug use).[11] CM may as well reduce the economic stressor for smoking cessation (e.g., unemployment) in HIV patients. [12,13] Yet, no studies to date tested CM to promote smoking cessation among HIV smokers. In our survey among HIV smokers, 45.7% were interested in CM to quit smoking. Therefore, CM may serve as an ideal adjunct intervention to MT to promote long-term abstinence in HIV smokers.

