Participants in this arm will attend an orientation session via Zoom that will last 60-90 minutes. They will connect with a research associate 3 times per week for 3 weeks after quit date via zoom where they will answer a few questions about their quitting progress, report on past 7-day smoking, and provide a sample of CO to verify their smoking status after their quit date using a portable CO monitor (coVita iCO™ Smokerlyzers®) and/or NicoTests saliva screen test that has been mailed to them. Those who proved their abstinence (CO< 8 ppm using coVita iCO™ Smokerlyzers®) and/or 30 ng/mL using NicAlert) [14] will receive a cash reward. The first successful CO sample earns \$5 cash, and then the reward increases by \$2 for each consecutive successful CO and/or saliva sample (e.g., \$5, \$7, \$9...). Participants also earn \$2 bonus for 4 consecutive successful CO and/or saliva samples (total=\$4). In all, participants can earn a maximum of \$176. Participant who fail the CO and/or saliva test will not receive reinforcement and the value of the next payment will be reset to the one that was missed.

Figure (1): overview of the study design

All participants will be asked to complete an end of treatment assessment 2 weeks after the intervention ends, which will be the same as the 3-month follow-up described below. Breath CO and/or saliva sample test (for cotinine analysis) will be collected at the end of treatment assessment via Zoom for participants who report they have quit.

All participants will be asked to complete a follow-up assessment 3 months after their quit date to assess their smoking status as well as get information about concomitant smoking and NRT use, use of additional NRT or cessation drugs (e.g., bupropion), and use of other tobacco methods. Breath CO and/or saliva sample test (for cotinine analysis) will be collected at the 3-month follow-up points for participants who report abstinence. The breath sample will be collected with the portable CO monitor (coVita iCO™ Smokerlyzers®) and/or NicoTests saliva screening test. A cut-off of 8 ppm for CO test (using coVita iCO™ Smokerlyzers®) and/or ≤ 30 ng/mL for the saliva sample test (using NicoTests) will be used to determine abstinence (Benowitz et al 2002).

Study measures

1. Baseline Assessment: All study materials and instrument will be translated into Spanish.

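### The primary outcome has two unranked time points, but only the 3-month one can compare the dynamic strategies; the 4-week one is the Stage 2 tailoring measure and informs Stage 1 only

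*Combined protocol and SAP*

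**What the plan says.** - **Objective** (section 1): the trial is meant "to identify the optimal dynamic strategy to promote biomarker-confirmed smoking abstinence among people living with HIV (PLWH".
- **Primary outcome** (section 5, Primary Outcome Measure): "Primary Outcome Measure Title: Smoking cessation - 7-day point-prevalence abstinence", with biochemical confirmation and the timeframe "4 weeks (end of treatment), and 3 months".
- **Labels** (section 5, Study measures): abstinence is called the main cessation outcome twice, once with confirmation by "NicoTests saliva sample of ≤ 30 ng/mL at the 1-month follow up" and once by "NicoTests saliva sample of ≤ 30 ng/mL at the 3-month follow up" (or by breath CO).
- **Stage 2** (section 5): participants re-randomised to Switch or Continue are "those who have not quit at 1 month evaluation". Both options are then assessed at 3 months.
- **Size** (section 15): up to 100 participants, 50 per Stage 1 arm.
- **Analysis** (section 7, Data Management): no test, alpha or success criterion is given for abstinence, and no comparison of embedded strategies. Three-month cessation appears only as the response in an exploratory model of baseline predictors.

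Nothing in the document puts one time point first, requires both, or divides an error rate between them.

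**The concern.** A primary outcome should answer the trial's stated question. Here one of its two time points cannot, because it is taken before the treatments that distinguish the strategies have been given. The two time points can also disagree: CM might lead at 1 month and have lost the lead by 3 months. The plan would allow either to be reported as the primary finding.

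The trial is not blinded, and staff must score 1-month status to carry out the second randomisation. Early results are therefore known participant by participant before the 3-month data exist. Since section 7 does not fix which result is reported first, the choice could be made after results are known.

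**Working it through.** **1. Is the 4-week outcome the tailoring visit?** The Primary Outcome Measure equates 4 weeks with end of treatment. Study measures places the end-of-treatment assessment one month after the quit date. Stage 2 re-randomises on status at the 1-month evaluation. Read together, these are one visit. Two caveats apply:

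- The document does not say whether quit status for Stage 2 means verified 7-day abstinence. I assume it does.
- Section 5 also sets the end-of-treatment assessment 2 weeks after the intervention ends. For MT (eight twice-weekly sessions, quit date at the fourth), the last session is about 2 weeks after quitting, which gives 2 + 2 = 4 weeks. For CM (3 weeks of contacts after quitting), it gives 3 + 2 = 5 weeks. These statements need to be reconciled.

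**2. What can each time point compare?** Two first treatments times two Stage 2 options give 2 × 2 = 4 embedded strategies. For first treatment *a* and Stage 2 option *b*, let

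- r_a = probability of abstinence at 1 month,
- s_a = probability that a 1-month quitter is abstinent at 3 months,
- q_ab = probability that a 1-month non-quitter given option *b* is abstinent at 3 months.

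| Time point | Expected abstinence under strategy (a, b) | Switch minus Continue, same *a* |
|---|---|---|
| 1 month | r_a | r_a − r_a = 0 |
| 3 months | r_a·s_a + (1 − r_a)·q_ab | (1 − r_a)(q_a,switch − q_a,continue) |

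The zero follows from the design and needs no assumed rates. The 1-month result identifies r_MT − r_CM only. All four strategies can differ at 3 months.

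**3. Illustrative error rate.** The plan has no figure to reproduce: N = 100 comes with no alpha, power, effect size or rates. Suppose MT and CM were compared at two-sided 5% at each time point and either could count as success.

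Independent tests: 1 − 0.95² = 0.0975. For correlated normal test statistics:

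| Correlation | 0.3 | 0.5 | 0.7 | 0.9 |
|---|---|---|---|---|
| P(at least one significant) | 0.0951 | 0.0907 | 0.0835 | 0.0704 |

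Simulated null trials (50 per arm, 100,000 runs, pooled z-test), with 3-month status depending on 1-month status and all rates assumed:

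| Abstinent at 1 month | Of these, still abstinent at 3 months | Late quitters | Correlation of tests | Either significant |
|---|---|---|---|---|
| 20% | 50% | 15% | 0.33 | 0.0977 |
| 25% | 60% | 10% | 0.52 | 0.0934 |
| 30% | 70% | 10% | 0.61 | 0.0865 |
| 30% | 80% | 5% | 0.77 | 0.0799 |

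The simulated range is 8.0% to 9.8%, against about 5% for one time point. It describes the two-arm MT-versus-CM contrast. It does not model Stage 2 re-randomisation and does not measure the problem in step 2.

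**4. Information available for strategies.** With assumed 1-month non-response of 60% to 90% and equal Stage 2 allocation (ratio not stated), each Stage 2 cell holds 25 × 0.6 = 15 to 25 × 0.9 = 22.5 participants. For the two-arm contrast with 50 per arm and assumed rates of 20% and 40%, power is 59% at 0.05 and 48% at 0.025.

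**The case against.** The strongest reply is that this is a pilot with no alpha, hypothesis test or success rule, so no error rate can be inflated. That stands as far as it goes. A reader might infer from step 3 that the plan exceeds a 5% error rate, but the document sets no such rate, so the figures are illustrative only. The mismatch in step 2 does not depend on them.

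A second reply is that 4-week abstinence is a sound endpoint. MT versus CM is randomised in Stage 1, section 4 lists two arms, and the background speaks of potential efficacy of the mindfulness intervention. This also stands. A reader might infer that the early result is invalid or unavailable for some strategies. It is neither: all participants are asked to complete that assessment, and it validly compares the first-stage treatments. Its limit is that it cannot discriminate within a Stage 1 arm.

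A third tempting reading is that the early result is taken while cash is on offer. The CM text says "They will connect with a research associate 3 times per week for 3 weeks after quit date", so a 7-day look-back at 4 weeks covers about days 21 to 28, after those contacts end. The secondary adherence outcome counts 12 CM check-ins, whereas 3 × 3 = 9, so the schedule itself needs reconciling and cannot carry the argument. Proximity to payment also cuts the other way: MT non-quitters who switch receive CM after month 1, nearer to the 3-month visit.

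Finally, replacing a primary time point in version 12 could itself look selective if data have accrued. That is a reason to document the change, not to leave the ambiguity.

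**Conclusion.** The point holds. The two primary time points answer different questions and are not ranked, and only 3 months addresses the stated objective. Following the plan as written, a Stage 1 comparison could stand as the primary answer to a question about dynamic strategies.

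This rests on reading the 4-week outcome as the 1-month tailoring visit, which the end-of-treatment label supports. The 8–10% figure rests on assumed two-sided 5% tests of MT versus CM and on assumed rates; it would be nearer 7% if the two tests were correlated at 0.9. The documents do not support a finding that a stated error rate is breached, or that the 4-week result is worthless. The correction should be made: it needs no new data and determines which result answers the trial's question.

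**What to change.** 1. **Section 5, Primary Outcome Measure:** name verified 7-day abstinence at 3 months as the single primary outcome, compared across the four embedded strategies.
2. **Section 5, Study measures and outcome list:** label 1-month abstinence as the Stage 2 tailoring variable and a secondary Stage 1 MT-versus-CM outcome. Say whether the tailoring rule uses verified status.
3. **Section 7:** add the strategy comparison, without which step 1 does not answer the objective. One suitable form estimates 3-month abstinence under each strategy with confidence intervals, using inverse-probability weights and robust standard errors. With equal allocation at both stages, 1-month quitters get weight 1/(1/2) = 2 and non-quitters 1/(1/2 × 1/2) = 4. Given the cell sizes above, present it as estimation.
4. **Timing:** reconcile the statements on when the end-of-treatment assessment occurs and state the anchor for 4 weeks.
5. **Record** the date of the change, the reason, and whether any outcome data had been seen. Align the registry entry if it lists both time points; it was not available for this review.

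If the team prefers to keep both as primary, it should assign each to its own question and either set a testing order, split alpha (0.025 each), or declare the analysis estimation only. The split lowers power, as step 4 shows.

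The changes are to text and analysis specification, with no new visits or data. The real cost is that an early CM advantage could be reported only as a secondary Stage 1 result.
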